Mental health services in Nigeria are deficient in quantity and quality. It is estimated that there is currently one psychiatrist to one million inhabitants and 40:1,000,000 for psychiatric nurses. [21] Furthermore, distribution of the available professionals is grossly skewed in favour of urban areas. The organization of mental health services is top-heavy; at the apex of the pyramid are 8 federal neuro-psychiatric hospitals and about 20 departments of Psychiatry at University Teaching Hospitals. Referral systems are cumbersome and not patient-friendly. Health workers at the secondary and primary levels including Doctors and Nurses have little practical training in or awareness of mental health issues. This leaves majority of rural dwellers who constitute majority of the population underserved. The notion of universal coverage and the Sustainable Development Goal mantra of 'leaving no one behind' will remain unattainable if these circumstances persist.

Study design

This is a cluster-randomized trial involving ten LGAs with the highest number of notified leprosy or BU cases between 2014 and 2018, purposively selected from 220 LGAs in south-east/south-south Nigeria. Five LGAs namely, Ebonyi, Ogoja, Ogbaru, Ogbia and Calabar South were randomized as intervention LGAs and five comparable LGAs – Etinan, Ethiope East, Obubra, Anambra East and Isoko South will serve as control. For allocation of clusters (LGAs) to intervention and control groups, a computer-generated list of random numbers was used.

Baseline survey will be done in the first year of the project in both intervention and control LGAs to determine the magnitude of depression using Patient Health Questionnaire-9 (PHQ-9); generalized anxiety disorders using Generalized Anxiety Disorders-7 (GAD-7), self-stigma using Stigma Assessment and Reduction of Impact (SARI) scale and quality of life using WHOQOL-BREF and Warwick-Edinburgh Mental Well-being Scale (WEMWBS) among eligible persons affected by leprosy/BU.

Attitude of health workers and community leaders towards leprosy/BU patients will be assessed using Focus Group Discussions (FGDs) and Key Informant Interviews (KII). Additionally, social distance scale (SDS) will also be used for community leaders.

Intervention

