Community opinion leaders will serve as lay-counsellors for patients with mental health disorders. These may include religious leaders, school teachers, retired civil servants, youth and women leaders and other respected members of the community. At least five lay-counsellors will be selected per LGA.

The primary healthcare workers include nurses and community health officers(CHOs). They will work with community leaders to provide mental healthcare in form of pharmacotherapy and psychotherapy to diagnosed patients as well as ensure referral to psychiatrist/clinical psychologist whenever necessary. At least five healthcare workers will be recruited per LGA.

Inclusion criteria

- Any person affected by leprosy/BU
- All persons affected by leprosy/BU registered for treatment from 2014 up to one year before end of intervention.
- Participants aged between 15 to 65 years.

Exclusion criteria

- Refusal to give consent
- Patients who need urgent medical attention
- Patients unable to communicate clearly

Sample size calculation

A study in Nigeria revealed that 58% of leprosy patients have mental disorders. [4] This study anticipates that 50% of respondents will have mental disorders and 35% reduction is desired after intervention. A study demonstrated that training of community lay-workers could reduce prevalence of depression by more than 20%. [15] A World Bank study revealed 22% of Nigerians are depressed.[22] Therefore, sample size calculation for matched pairing at power=80%; p=0.05 and anticipated 30% loss to follow up is 400 leprosy patients (200 each group: intervention/control). Calculation was powered by leprosy alone, because data on mental disorders among BU patients are unavailable. However, it is known that many features (disfigurements and

stigma) known to result in mental health disorders are similar in both diseases. All eligible BU patients will be included.

2.5.6 Data collection methods:

Data will be collected from persons affected by leprosy/BU at baseline and post intervention and from community leaders and healthcare workers in intervention and control LGAs. Data collection tools include: PHQ-9, GAD-7, WEMWBS, SARI stigma scale, WHOQOL-BREF, SDS, FGD/KII guides, Log-books kept by community leaders and SHGs and registers for routine leprosy/BU data collection. Data will include:

- Bio-demographic information

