- Prevalence of mental disorders among persons affected by Leprosy/BU using PHQ-9 as screening tool for depression and GAD-7 (see annex for tools) to screen for GAD.
- Attitude of community leaders towards leprosy/BU patients using SDS and FGD/KII.
- Stigma perception among persons affected by leprosy/BU using SARI Stigma scale
- Quality of life and mental well-being of persons affected by leprosy/ BU using WHOQOL-BREF and WEMWBS.
- Perception of healthcare workers on mental well-being of leprosy/BU patients using FGD/KII.

The study and control groups will be compared after intervention to determine change in mental health status, quality of life and social participation of study participants.

Data quality will be guaranteed by:

- Training and supervision of research assistants
- Double transcription of voice recordings of KIIs and FGDs

Validation of study tools

Prior to field work, a short validation will be done to validate the WEMWBS tool in all relevant study sites in Nigeria.

This involves:

- Translation/back-translation of tool in Pidgin English, Igbo and Efik languages
- Conduct interviews to ascertain how well tool is understood (interpretability).
- Several rounds of translation/back-translation with 5-10 persons.

• Further validation will be done during field work.

Recruitment

To recruit study participants, first, names and contact details of leprosy or BU patients will be obtained from LGA Leprosy and Buruli ulcer Treatment Registers, respectively. Eligible persons will be contacted by phone calls through the LGA Tuberculosis and Leprosy Supervisors (LGTBLS) and invited for orientation meeting on a scheduled date. Newly detected, eligible leprosy or BU patients registered for treatment at the health facilities during intervention will also be evaluated for depression and GAD by healthcare workers using the research tools and thereafter introduced to nearby SHGs. All leprosy/BU patients who are eligible regardless of mental health status will be enrolled into SHGs up to one year before end of intervention. However, patients who come after the deadline will join the SHGs and receive appropriate services, but not included in final research analysis. All suspected cases of BU or leprosy found by community leaders or members of SHGs will be referred to health workers for diagnosis.

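### The arms are compared by an unadjusted test on leprosy and Buruli ulcer patients pooled, so a chance difference in disease mix between five and five LGAs can enter the effect estimate; disease should be a prespecified stratum or covariate

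*Protocol*

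**What the plan says.** Four parts of the protocol bear on this.

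- **Study design.** The trial takes "ten LGAs with the highest number of notified leprosy or BU cases between 2014 and 2018" from 220 candidate LGAs. An LGA can therefore qualify through leprosy, BU or both. For the five-against-five allocation, "a computer-generated list of random numbers was used". No stratification or matching on disease is described. The controls are called "five comparable LGAs", without saying in what respect.
- **Sample size calculation.** The figure is 400 leprosy patients, 200 per group, at 80% power with 30% loss to follow-up. The stated basis is: "This study anticipates that 50% of respondents will have mental disorders and 35% reduction is desired after intervention". The section adds: "Calculation was powered by leprosy alone, because data on mental disorders among BU patients are unavailable". It then argues that disfigurement and stigma, which contribute to mental disorder, are common to both diseases, and ends: "All eligible BU patients will be included". No number of BU patients is given.
- **2.5.6 Data collection methods.** "The study and control groups will be compared after intervention to determine change in mental health status, quality of life and social participation of study" […]. The groups are taken whole.
- **Data management.** Between study and control groups, categorical outcomes get a chi-square test and continuous outcomes a Student t test. The only regression is a logistic model for predictors of outcome, with variables admitted by a bivariate p value below 0.2. Disease is not named in it, and it is not presented as the comparison of arms.

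**The concern.** The protocol says it has no data on mental disorders in BU. It argues that contributing causes are similar, which is a fair reason to include BU patients but does not establish that prevalence is equal. Because an LGA could be selected on either disease, the BU share is plausibly a feature of the LGA, and ten LGAs do not reliably balance such a feature.

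If prevalence of depression or anxiety differs by disease and the arms differ in BU share, a pooled test without disease in it counts part of the disease difference as an intervention effect, or hides part of a real one. The test has been written down, so this concerns a stated choice and not a detail left to the statistical analysis plan.

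**Working it through.** **1. The plan's own figure.** The document gives 50% prevalence, a 35% reduction, 80% power, p = 0.05, 30% loss and 200 per group. It does not say whether 35% is relative. Read as relative (50% to 32.5%), the two-sided unmatched two-proportion formula gives 124 per group, or 124/0.7 = 178 after loss. With continuity correction it gives 135, or 193 after loss. The text says matched pairing, which needs a within-pair correlation that it does not state, so 200 is approached but not reproduced exactly. Nothing below depends on that; 200 is used only to get completers, 200 × 0.7 = 140 per group.

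**2. Yardstick.** Individual-level standard error of the difference with 140 per group: √[(0.50 × 0.50 + 0.325 × 0.675)/140] = √(0.4694/140) = 0.058, or 5.8 points. The planned effect on this reading is 17.5 points. The 5.8 ignores clustering, which would raise it, and the added BU patients, who would lower it; the document gives no figure for either.

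**3. The error term.** Let s be an arm's BU share and g the leprosy prevalence minus the BU prevalence. With no intervention effect, an arm's pooled prevalence is (leprosy prevalence) − s × g. The crude difference between arms is then, in size,

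error = (difference in BU share) × g.

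It is zero if g = 0 or the shares are equal, and it can have either sign.

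**4. How far shares may differ.** With equal-sized LGAs, SD(difference in mean share) = SD(LGA share) × √(2/5). The protocol gives no shares, so three spreads are assumed.

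| Assumed spread of LGA BU shares | SD of LGA share | SD of arm difference | SD of error, g = 10 points | SD of error, g = 20 points |
|---|---|---|---|---|
| Moderate, Beta(2,4) | 0.178 | 0.11 | 1.1 | 2.3 |
| Uniform, 0 to 100% | 0.289 | 0.18 | 1.8 | 3.7 |
| Mostly one disease per LGA, Beta(0.5,0.5) | 0.354 | 0.22 | 2.2 | 4.5 |

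The gaps of 10 and 20 points are also assumptions. The SD of the error is thus about 1 to 4.5 points.

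**5. Against the yardstick.** In the uniform case, the total SD is √(5.8² + 1.8²) = 6.1 to √(5.8² + 3.7²) = 6.9 points, a rise of 5% to 19%.

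**6. Given a particular imbalance.** With 50% prevalence in both arms, the standard error is √(2 × 0.25/140) = 6.0 points. A share difference of 20% with a 20-point gap shifts the estimate by 4.0 points, and the chance of p < 0.05 with no intervention effect becomes about 10%. A share difference of 30% with the same gap gives 6.0 points and about 17%. A share difference of 10% with a 10-point gap gives 1.0 point and leaves it at about 5%. Clustering is ignored throughout.

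**7. Effect of the remedy.** Comparing arms within disease, or adjusting for disease, removes the term in step 3.

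**The case against.** **A reader might infer that the plan is sized for the wrong population.** The documents do not support this. The protocol says openly that the 400 are leprosy patients and that BU patients are included as well. Enrolling a second group on top of a powered one does not by itself lower power. Nor is the 50% simply the leprosy figure: the cited leprosy study gives 58%, and 50% is what the trial anticipates among respondents.

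**A reader might infer systematic bias.** The LGAs were randomised, so a difference in disease mix is chance imbalance, one part of between-LGA variation alongside age, disability and much else. It therefore overlaps with the wider question of tests that treat patients as independent. This stands, and it limits the point to precision and to the reading of one realised allocation. Disease still differs from other covariates: it determined which LGAs were eligible, and the protocol says its relation to the outcome is unknown.

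**A reader might take the 22% depression figure as a BU prevalence and arrive at a 28-point gap.** That figure is for Nigerians in general and for depression only. It is no evidence about BU.

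**The plan may already deal with it.** Section 2.5.6 speaks of determining change, and assessments are repeated after the intervention. If change from baseline is compared between arms, a stable gap between diseases largely cancels. But the between-arm tests under Data management are not said to be on change. The predictor model could admit disease through its p-value screen, but only as the data happen to fall, and it is not the arm comparison.

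**Covariates usually belong in the statistical analysis plan.** True, and one may name disease. The protocol nevertheless specifies the between-arm test, and as written it is pooled and unadjusted.

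**Conclusion.** The point holds as a worthwhile improvement to a stated method. The between-arm test pools two diseases without a disease term, the LGAs were selected on either disease, and equal prevalence of mental disorder is not established.

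The size of the error cannot be computed from the protocol. On assumed LGA spreads and an assumed 10 to 20 point gap, its SD is about 1 to 4.5 points, against an individual-level standard error of about 5.8 and a planned effect of 17.5 if the 35% is relative. That is modest in most allocations and material in an unlucky one. It is zero without a prevalence gap and smaller if change is analysed. The wording is certain; the size is not.

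The point does not extend to the sample size or the stated power. Sizing on leprosy is disclosed and is not an error.

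**What to change.** In Data management, or in the statistical analysis plan before outcomes are examined by arm:

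- Name disease (leprosy or BU) as a stratum or covariate in the main between-arm comparison of each outcome.
- Use a form that respects the LGA clusters. One option is a two-stage analysis: regress the outcome on disease without arm, then compare the ten LGA-level residuals between arms. Another is a mixed model with a random LGA effect and a small-sample correction.
- Report the leprosy-only effect, the population used for sizing, beside the combined effect, with both specified in advance so that neither is chosen afterwards.
- Tabulate the numbers of leprosy and BU patients by LGA and arm, so that the realised mix is visible.

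Disease is known from the separate leprosy and BU treatment registers named under Recruitment. The cost is a few sentences and one covariate: no new data, no further patients and no change to the sample size. One caution: if most LGAs hold mainly one disease, adjustment leans on differences between LGAs, and the leprosy-only result will rest on few well-filled LGAs. The table by LGA will show whether that is so.

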Two research assistants per LGA comprising members of the selected communities will be trained for one day for data collection using the interviewer administered questionnaire. The research assistants must have attained at least secondary education. They will be trained on privacy and confidentiality before the study begins. The researchers will conduct the FGDs and KIIs. Interviewers will be trained on confidentiality procedures and undertake to ensure confidentiality as part of their engagement agreement.

A secured box will be made available in German Leprosy and TB Relief Association head office for the safe storage of the questionnaires and other materials related to the research. The recordings used for FGDs and KIIs will be transcribed immediately after the interview. English, Pidgin English, Efik or Igbo languages will be used to conduct FGDs and the discussions will take place in secluded areas of the selected communities like public primary schools and town halls.

Data entry and analysis for (quantitative data collection method) will be done using IBM Statistical Package for Social Sciences (SPSS) statistical software version 25. Categorical variables among the study and control groups will be compared using Chi square test of statistical significance while continuous variables will be compared using Student t test. In between group comparisons (like study group before and after intervention) will be done using Mcnemar Chi square test for categorical variables and the dependent Student t test for continuous variables. In determining predictors of the outcome variables, independent variables that have a p value of less than 0.2 on bivariate analysis will be entered into the logistic regression model. The result of the logistic regression analysis will be reported using adjusted odds ratio and 95% confidence interval and the level of statistical significance will be determined by a p value of <0.05.

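### PHQ-9 and GAD-7 are collected as scores but framed only as a prevalence, with logistic regression the only model for predictors; the total scores should be analysed as well

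*Protocol*

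**What the plan says.** Under 2.5.6 Data collection methods, the item for depression and anxiety reads "Prevalence of mental disorders among persons affected by Leprosy/BU using PHQ-9 as screening tool for depression and GAD-7". The same list names stigma, quality of life and well-being by their scales, without turning them into a prevalence. The section then says that the arms will be compared after the intervention for change in mental health status. It does not say whether that means a score or a proportion.

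The Sample size calculation works on a proportion: "This study anticipates that 50% of respondents will have mental disorders and 35% reduction is desired after intervention". It gives "sample size calculation for matched pairing at power=80%; p=0.05 and anticipated 30% loss to follow up is 400 leprosy patients", that is, "200 each group: intervention/control". No cut-off on either scale appears there or elsewhere.

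Data management sets general rules. For the arm comparison, "Categorical variables among the study and control groups will be compared using Chi square test of statistical significance", and continuous variables go to a Student t test. Neither scale is named under either rule. For predictors of the outcome variables, the only model is logistic: "The result of the logistic regression analysis will be reported using adjusted odds ratio and 95% confidence interval". Secondary objectives 5 and 6, on socio-demographic variables and physical impairment as determinants of depression and anxiety status, fall under that sentence.

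**The concern.** Each questionnaire yields a total for every participant. Once the total is cut, a person who improves from severe to moderate symptoms but stays above the cut counts as unchanged, while a one-point move across the cut counts as full success. The objectives ask about mental health status, which does not require a cut.

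Two things are at stake. For the arm comparison, a trial of ten LGAs has little information to spare, and the text leaves it unclear whether the totals will be compared at all. For objectives 5 and 6 the position is clearer: a logistic model needs a binary outcome, so the totals must be cut there, and associations with impairment or socio-demographic factors are estimated from less information than was collected.

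**Working it through.** **Inputs from the protocol.** 50% with mental disorders; 35% reduction; 80% power; p = 0.05; 30% loss; 200 per arm; ten LGAs, five per arm. Analysed per arm: 200 × (1 − 0.30) = 140, or 28 per LGA.

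**Assumptions (not in the protocol).** Two-sided test; the form of the score distribution; the intra-cluster correlation (ICC). The 35% can be read as relative (50% to 32.5%), as the end rate (50% to 35%) or as absolute (50% to 15%).

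**The stated 400.** It is not reproduced exactly. The usual two-proportion formula for 50% v 32.5% gives 124 per arm, and 124/0.7 = 178 (356 in total). With continuity correction it gives 135 per arm, and 135/0.7 = 193 (386 in total), 3.5% below 400. For 50% v 35% without correction it gives 170/0.7 = 243 per arm (486); for 50% v 15%, 27/0.7 = 39 per arm (78). The relative reading lies closest to 400. The protocol mentions matched pairing but gives no correlation or discordance rate from which to check that version.

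**Power for the cut, 140 per arm, no clustering.**
Power = Φ{[(p1 − p2)√n − 1.96√(2p̄(1 − p̄))] / √(p1(1 − p1) + p2(1 − p2))}, with p̄ the mean of p1 and p2.
- 50% v 32.5%: (0.175 × 11.832 − 1.96 × 0.6962)/0.6851 = 1.03, so 85%.
- 50% v 35%: (0.15 × 11.832 − 1.96 × 0.6991)/0.6910 = 0.585, so 72%.

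**Power for the score, same n.** Assume a normal score with SD 1 and a fixed cut at the control median, the whole distribution shifting by d = −Φ⁻¹(p2). Power ≈ Φ(d√(n/2) − 1.96).
- 32.5%: d = 0.454; 0.454 × 8.367 − 1.96 = 1.84, so 97%.
- 35%: d = 0.385; 0.385 × 8.367 − 1.96 = 1.26, so 90%.

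**How far this carries.**

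| Scenario | Cut | Score |
|---|---|---|
| 50% v 32.5%, 140 per arm | 85% | 97% |
| 50% v 35%, 140 per arm | 72% | 90% |
| 50% v 32.5%, 200 per arm (no loss) | 95% | 99% |
| 50% v 15%, 140 per arm | about 100% | about 100% |
| 50% v 32.5%, cluster-level t test on 8 df, ICC 0.01 | 65% | 84% |
| Same, ICC 0.05 | 41% | 59% |

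The cluster rows use a design effect of 1 + 27 × ICC and the same ICC for both outcomes. Simulated skewed scores (negative binomial, truncated at 27, cut at 10) under a shift gave 84–85% v 96% for 32.5%, and about 71% v 89–90% for 35%.

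**A different pattern of benefit.** Suppose 35% of the people above the cut move to scores typical of those below it, and nobody else changes. Prevalence again goes from 50% to 32.5%. Simulation at 140 per arm (6,000 trials per scenario, no clustering) gives about 84% for chi-square and 67% for the t test with a normal score. With negative binomial scores cut at 5 or 10 (dispersion 1, 2 and 4), it gives about 84–85% and 62–73%. The cut is then the more powerful outcome.

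**The case against.** The strongest case is that nothing in the protocol excludes the totals. Data management assigns continuous variables to a t test, and a total score can be treated as one. The prevalence item sits in a list of data to be collected and suits objective 1, the magnitude of disorder. Variable-by-variable assignment and the cut-off may be in a statistical analysis plan that is not shown. Prevalence also has merit as a target: the stated aim is fewer mental disorders, the result is meant for a national programme, and it matches the sample size. Finally, counselling and treatment are directed at people found to have a disorder, so benefit may concentrate above the cut, although the self-help groups take everyone.

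Most of this stands. A reader might infer that the protocol commits the arm comparison to chi-square alone and so forfeits 12 to 17 points of power on its own assumptions. The documents do not support that. The t test is available, logistic regression is for predictors and not for the arm comparison, and the protocol gives no score distribution, SD or ICC. Nor is there always a gain of at least 5 points: it is about nil for 50% v 15%, just under 5 points at 200 per arm for 50% v 32.5%, and negative when benefit is confined to cases. Any Buruli ulcer patients enrolled beyond the 400 would also raise the analysed number above 140 per arm.

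What the objection does not remove is that the protocol itself frames both outcomes as a proportion, sizes the trial on one, and offers only a logistic model for predictors.

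**Conclusion.** The point holds as a modest, inexpensive improvement. The binary framing of depression and anxiety is in the text, and for objectives 5 and 6 the only model named requires the scores to be cut. For the arm comparison, the text leaves open whether the totals are used.

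If only the dichotomy is tested, the loss is about 12 points (85% v 97%) for 50% v 32.5%, or about 18 points (72% v 90%) for 50% v 35%. This assumes 140 per arm, no clustering, a two-sided test and a normal score that shifts as a whole. Because the ordering can reverse, the calculation supports reporting both outcomes, not replacing the prevalence. Clustering matters more for absolute power: at an assumed ICC of 0.05, a cluster-level test of the cut has about 41%. That is a separate matter.

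**What to change.** 1. In 2.5.6 Data collection methods and in Data management, state that PHQ-9 and GAD-7 total scores after the intervention are compared between arms as a mean difference with 95% CI, by the cluster-valid method adopted for the trial.
2. Alongside this, report the prevalence at a cut-off stated in advance for each scale. The prevalence remains the basis of the sample size and of objective 1, so the Sample size calculation need not be rebuilt on a score.
3. Fix both results as planned, so that neither is chosen after the data are seen.
4. For objectives 5 and 6, fit a linear model to each total score and keep the logistic model as a supporting analysis.

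The cost is wording only: no new data, participants or visits. The downside is a second stated result for each scale, and a mean difference that is harder to convey to the control programme than a prevalence.
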